| 7 | Data Management Plan | 22 |
| 7.1 | Data Collection | 22 |
| 7.2 | Data Management | 22 |
| 7.3 | Data Storage | 22 |
| 8 | Assessment of Safety | 22 |
| 9 | Clinical Monitoring | 23 |
| 10 | Statistical Considerations | 23 |
| 10.1 | Study Outcome Measures and Analysis | 23 |
| 10.2 | Sample Size Considerations | 24 |
| 11 | Ethical Considerations | 24 |
| 11.1 | Subject Confidentiality | 24 |
| 11.2 | Future Use of Stored Specimens | 24 |
| 11.3 | Informed Consent Process | 25 |
| 12 | Literature References | 25 |

Protocol Summary

Title: Evaluation of host biomarker-based point-of-care tests for targeted screening for active TB (Screen TB)

Population: A total of 800 people presenting at primary health care clinics with presumed active pulmonary tuberculosis, aged 18 to 70 years, male or female gender, will be recruited. They should be willing to give informed, written consent, including consent for HIV testing. They should have symptoms that could be compatible with active TB (cough > two weeks, plus at least one of the following: fever, weight loss, hemoptysis and night sweats). Participants should not have been on TB treatment for the past 90 days and should not have received immune suppressive therapy, be known with alcohol of drug abuse or have a haemoglobin level <10g/dl. HIV co-infection is not an exclusion criterion. Participants will be recruited from primary health care clinics in Cape Town, South Africa, Windhoek in Namibia, Addis Ababa in Ethiopia, Banjul in The Gambia and Kampala in Uganda.

Number of Sites: See Section 1

Study Duration: 3 years

Subject Duration: 6 months for TB cases, 2 months for non-TB cases

Objectives:

The overall objective of the study is to incorporate a six-marker serum signature into a multiplex UCP-LFA format, referred to as TransDot, for finger-prick blood testing. The end point of the study is the accuracy (sensitivity and specificity) of the UCP-LFA TransDot test on finger-prick blood for active TB and will be prospectively compared against gold standard composite diagnostic criteria (GeneXpert, MGIT culture, TB sputum smear, CXR, TB symptom screen and response to TB treatment).

Primary:

• The primary outcome of interest will be accuracy, sensitivity and specificity of the TransDot fingerprick test when compared with the composite gold standard tests.

Secondary:

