5. STUDY POPULATION

5.1 SELECTION OF THE STUDY POPULATION

Adult participants with presumed active TB disease will be recruited in South Africa, the Gambia, Uganda, Namibia and Ethiopia. Each site will recruit approximately 160 participants with suspected TB, but faster recruiting sites may recruit more and slower recruiting sites fewer, until the desired overall total of about 800 participants is reached. In South Africa, up to 300 participants will be recruited from primary health care clinics in Cape Town.

Patients presenting to the health care facility with symptomatic pulmonary disease and a high likelihood of having tuberculosis will be enrolled and followed up for outcome classification.

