6 STUDY PROCEDURES/EVALUATIONS

6.1 STUDY PROCEDURES

Patients who present to a primary health care clinic with pulmonary symptoms and who are presumed to have TB disease, will be approached to participate in the study by research recruiters or nurses. Sputum results from the National Health Laboratory System may also be accessed to identify patients who were investigated for TB.

Participants will be recruited into either the training or the test cohort, with the test cohort recruitment starting after the training cohort has completed the enrolment of 500 participants. Participants will be required to attend the baseline visit, a week 2 visit (to review results and antibiotic response in those not already diagnosed with TB at this point), a week 8 visit (all participants, to assess TB treatment response in TB cases and to assess alternative diagnosis or resolution of symptoms in non-TB cases) and a week 24 visit (TB participants only, to assure TB was treated successfully).

Willing and eligible patients will be informed about the study by a research nurse, guided by the informed consent document, and asked to sign the document, after being given the opportunity to ask questions. The participant will receive a copy of the informed consent form, while the original consent form will be filed in the regulatory file and another copy will be filed in the participant's file. Each recruited participant will be assigned a unique study ID number by the recruiting nurse.

Personal and demographic information on each participant will be collected by the nurse using an electronic case report form on a tablet computer. Information such as name, address, telephone numbers, other contact person, age, sex, ethnicity, language and employment will be collected and uploaded to a secure, password protected and centralized database hosted at Stellenbosch University.

Standardized TB symptoms case report forms and medical history case report forms will be completed for all participants at each visit by the research nurse and recorded electronically via the tablet into the database. Information collected will include TB symptoms presence, severity and duration, previous TB episodes and treatment outcome, other medical conditions, medication use, HIV status (if known), previous surgery, family history, smoking history, alcohol consumption and recreational drug usage.

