For test set participants, serum will be collected for local laboratory based TransDot tests. POC TransDot tests will also be performed on fingerprick blood by the research nurse in a standardized manner across sites, at the baseline visit and before any results from the composite gold standard tests are available. A drop of blood will be applied to the test strip and the test strip will be submitted to the reader. The reported result will be recorded in the case report form. Agreement between the laboratory based and point of care TransDot tests will be calculated. Study investigators will be blinded to the TransDot test results until the final outcome classification has been completed for each participant. TransDot test results will also not be shared with clinic staff and no clinical decisions will be made based on TransDot test results.

A TransDot test will also be done at weeks 8 and 24 to investigate the utility of the test for monitoring treatment response as a secondary outcome. It will be compared to week 8 and 24 treatment outcomes as defined by sputum results, radiology, where applicable and TB symptoms.

It is expected that approximately one third of the participants will have a final diagnosis of active TB, whereas the non-TB cases will have a range of conditions including viral and bacterial lower respiratory tract infections and non-infectious conditions like chronic obstructive pulmonary disease.

The decision to treat for TB and the administration of treatment will remain the responsibility of the national healthcare system, although all relevant results to aid the decision will be shared with clinic staff. Referrals to the appropriate level of care for any accidental discoveries of other conditions or positive HIV results will also be done by the research team.

Participants at Stellenbosch University will receive R150 for participation in the study to compensate for travel expenses and loss of hours at work.

6.2 STUDY SCHEDULE:

Baseline visit (all participants)

Obtain written informed consent. Assign unique study participant ID. Conduct TB symptoms questionnaire. Obtain relevant medical history. Perform directed physical examination. Collect sputum samples for smear (except if results are obtainable from the government clinic), GeneXpert, MGIT culture and storage. Perform chest x-ray.

Perform pre- and post-test counselling for HIV test, except in participants who disclose their known positive status to study nurses.

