10. STATISTICAL CONSIDERATIONS

10.1 STUDY OUTCOME MEASURES AND ANALYSIS

The main outcomes of interest are sensitivity and specificity of the point of care TransDot test during phase 3 of this study. Sensitivity will be calculated as the proportion of true positives (as determined by the composite gold standard of TB case definitions), who test positive on the TransDot test. Specificity will be calculated as the proportion of true negatives who test negative on the TransDot test.

For the primary analysis, the true positives as determined by the composite gold standard of TB case definitions, will consist of the Definite and Probable TB classes. The Possible TB class will be excluded as their diagnosis may involve a significant amount of uncertainty. This group will be included in a secondary analysis to show the TransDot test's performance in this uncertain group of participants.

Secondary outcomes of interest are positive and negative predictive values of the TransDot test, which will be calculated as the proportion of participants with positive or negative tests who are positive or negative according to case definitions, respectively.

Sensitivity, specificity, positive and negative predictive values will be reported with 95% confidence intervals.

Reproducibility of the test will be determined between laboratory based tests and point of care tests, as well as between the point of care tests conducted in the different countries, using the Kappa statistic for agreement.

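### Section 6.1 lets existing sputum results be used to find test-set recruits, which conflicts with its own rule that TransDot is run before any composite reference result is available

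*Combined protocol and SAP*

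**What the plan says.** **Recruitment.** Section 6.1 describes the main route as "Patients who present to a primary health care clinic with pulmonary symptoms and who are presumed to have TB disease". It then adds a second route: "Sputum results from the National Health Laboratory System may also be accessed to identify patients who were investigated for TB". The next paragraph of that section covers recruitment into both the training and the test cohort, and nothing confines the second route to either one. Consecutive enrolment is not stated anywhere.

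**Timing of the index test.** For the test set, Section 6.1 (Fingerprick TransDot test) has the nurse perform the point-of-care test "at the baseline visit and before any results from the composite gold standard tests are available".

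**Source of the smear.** The baseline schedule in Section 6.2 reads "Collect sputum samples for smear (except if results are obtainable from the government clinic"; Section 6.3.1 makes the same exception. GeneXpert and culture have no such exception.

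**Reference standard.** The Protocol Summary lists the composite as "GeneXpert, MGIT culture, TB sputum smear, CXR, TB symptom screen and response to TB treatment". The case-definition table in Section 4.2, which the outcome committee applies, has an AFB smear column.

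**Outcomes.** Section 10.1 makes sensitivity and specificity the main outcomes and adds: "Secondary outcomes of interest are positive and negative predictive values of the TransDot test". The predictive values are calculated directly from the participants recruited.

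**The concern.** TransDot is meant as a screening test that decides who goes on to sputum testing (Sections 2.1 and 3). Its intended users therefore have no sputum result yet. A test-set participant who was found from a sputum result already on file differs in two ways.

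First, a component of the reference may already be known when TransDot is run, which the timing rule does not allow. Second, and more important, the result may have influenced who was approached. If so, the mix of cases and non-cases in the test set could differ from that of unselected attendees. A different case mix could bias sensitivity and specificity. A different TB prevalence would change PPV and NPV even if sensitivity and specificity were untouched. Without a record of the recruitment route, none of this could be examined afterwards.

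**Working it through.** **Step 1. Can both rules hold?**

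- The laboratory-list route uses results that exist before the participant is approached, so before the baseline visit.
- The timing rule requires that no composite result is available when TransDot is run at that visit.
- Smear is a composite component in the Protocol Summary, Section 2.2 and the Section 4.2 table. Sections 3 and 4 omit it from their lists, but the table is what classifies participants.
- Sections 6.2 and 6.3.1 allow the outside smear to serve as the study's smear.

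So if a test-set participant is found through an issued smear result, that result can be the reference smear itself, and it is available before TransDot. The timing rule fails for that participant whether the smear was positive or negative.

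**Step 2. The plan's own figure.** Section 10.2 wants 100 TB cases with about one third TB: 100 / (1/3) = 300. This reproduces, and the recruitment question does not change it.

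**Step 3. Predictive values (illustration).** Inputs are the Section 4 target of sensitivity 0.90 and specificity 0.80, and a base prevalence of 1/3. The share w found through the laboratory list is assumed, because the documents give none.

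PPV = Se·p / [Se·p + (1 − Sp)(1 − p)]; NPV = Sp(1 − p) / [Sp(1 − p) + (1 − Se)p].

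If all listed recruits have TB, p = (1 − w)/3 + w. If none has TB, p = (1 − w)/3.

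| Assumption | p | PPV | NPV |
|---|---|---|---|
| w = 0 | 33.3% | 0.300/0.433 = 69.2% | 0.533/0.567 = 94.1% |
| w = 10%, all TB | 40.0% | 0.360/0.480 = 75.0% | 0.480/0.520 = 92.3% |
| w = 20%, all TB | 46.7% | 0.420/0.527 = 79.7% | 0.427/0.473 = 90.1% |
| w = 10%, none TB | 30.0% | 0.270/0.410 = 65.9% | 0.560/0.590 = 94.9% |
| w = 20%, none TB | 26.7% | 0.240/0.387 = 62.1% | 0.587/0.613 = 95.7% |

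The two halves of the table move in opposite directions. The text does not say which, if either, applies.

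**Step 4. Sensitivity (illustration).** Prevalence alone does not move sensitivity; case mix can. If a fraction f of cases comes from known results with sensitivity s1, and the rest have s0, the shift is f(s1 − s0). With assumed values, 0.10 × (0.93 − 0.87) = 0.6 points and 0.40 × (0.95 − 0.85) = 4.0 points. The same formula applies to specificity among non-cases, where the documents give no basis even for a sign.

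**The case against.** The strongest reply is that Section 6.1 speaks of patients who were investigated, not of those who tested positive. A list of everyone investigated includes negatives, so prevalence need not rise. The plan still expects about one third TB among participants (Sections 6.1 and 10.2). Section 5.2 also excludes people now or recently on TB treatment, which removes known positives who have already started. This stands. A reader might infer that recruiters will pick sputum-positive patients, but the documents do not say so. It does not remove the timing conflict, which exists for either result. Nor does it make the route neutral, because nothing requires listed patients to be approached regardless of result.

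Second, an outside smear seldom decides the reference class. In the Section 4.2 table, categories A and B do not use smear. C and E differ on it, but both count as TB in the primary analysis. Category D is the main place where a positive smear matters, although categories H and I (no TB) also require a negative one. In addition, a smear that can be obtained from the clinic need not have been issued before TransDot. Both remarks are fair. They limit the effect on classification but do not address selection.

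Third, a reader device gives the TransDot result, and investigators and the outcome committee are blinded to it. These safeguards limit bias in reading the strip and in classification. They do not govern who is enrolled.

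Fourth, even the assumed maximum of 4.0 points is below the roughly 5-point half-width implied by the plan's 85 to 95% interval. That is true, but a selection bias shifts the centre of the interval and does not shrink with more participants.

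**Conclusion.** The conflict is in the text and needs no assumed figure: as written, the laboratory-list route and the timing rule cannot both be met for test-set participants found through an issued smear result. The route may also select participants on a reference result. The size and direction of any effect on sensitivity, specificity, PPV and NPV are unknown. The figures above rest on assumed shares and sensitivities and show only what could happen.

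Two stronger readings are tempting and should not be drawn. One is that the accuracy estimates will be distorted: the documents give neither the share recruited this way nor a rule favouring positives, so this is a risk and not a demonstrated effect. The other is that Section 5.1, which says patients "with symptomatic pulmonary disease and a high likelihood of having tuberculosis will be enrolled", is part of the same contradiction or restricts the sample to clear-cut TB. A judged likelihood is not a reference result, so it does not breach the timing rule. The nearby text speaks of presumed or suspected TB, and one third TB does not fit a filter for obvious cases. The phrase is undefined and absent from the Section 5.2 criteria, which is a separate and minor inconsistency.

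The point still merits a change, because it concerns who enters the primary analysis and is cheap to settle before test-set recruitment.

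**What to change.** For the test set, reconcile the two statements in Section 6.1: enrol consecutive attendees who meet the Section 5.2 criteria, before any sputum result has been issued. Align the Section 5.1 wording with Section 5.2.

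If the laboratory-list route is still used in the test set, record the recruitment route and whether a sputum result had been issued before TransDot. Report sensitivity, specificity, PPV and NPV excluding those participants. PPV and NPV at other prevalences are optional reporting.

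Cost: wording, one CRF field and one extra analysis. Closing the route may slow test-set recruitment. Excluding flagged participants widens intervals slightly. Under the Step 3 scenario with 30 or 60 known positives set aside, 270/3 = 90 or 240/3 = 80 cases remain. The normal-approximation half-width at 90% sensitivity, 1.96 × √(0.9 × 0.1/n), would then be 6.2 or 6.6 points, against 5.9 points for 100 cases.

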4. STUDY DESIGN

A non-interventional, diagnostic, prospective cohort design will be utilized, incorporating two separate sets of participants – overall a training set of 500 and a test set of 300 participants. The purpose of the training set will be to optimize the TransDot test and Reader to excellent sensitivity (90% or above) and acceptable specificity (80%). The test set will then be utilized to evaluate the TransDot test accuracy on fingerprick blood at the point-of-care site in a laboratory-free manner on a new prospective cohort of participants.

Training set participants will be recruited and receive investigations for TB. Blood samples will also be collected from them for performance of ELISAs and laboratory-based TransDot tests. These blood samples will be drawn at baseline, week 8 and week 24 at end of treatment for confirmed TB cases and at baseline and for non-TB cases.

Test set participants will be recruited and receive investigations for TB. A POC TransDot test will be performed on fingerprick blood at baseline, and at week 8 and week 24 in participants on TB treatment, as well as a laboratory based TransDot test on serum at baseline. The week 8 and week 24 TransDot tests will be used to investigate the test's utility as an indicator of treatment response.

Follow up of both sets of participants will be to week 24 for those found to have active TB, and week 8 for those found to be non-TB cases. There will be study visits at baseline, week 2 (GeneXpert negative participants only), week 8 and week 24 (participants on TB treatment only).

The TransDot test will be evaluated against a composite gold standard in the form of previously developed case definitions, consisting of GeneXpert, MTB culture, CXR, TB symptoms, response to antibiotics and TB treatment response. The case definitions will be applied to participant data by an outcome classification committee (see 4.2) who will remain blinded to the TransDot results of the test set, until after completion of all participants' outcome classification.

The primary outcome of interest will be performance of the TransDot test as compared to the gold standard, measured by sensitivity and specificity.

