4.2 EVALUATION OF TB DIAGNOSIS

An outcome classification committee will classify each participant according to the standard case definitions below. The committee will consist of clinician investigators from the participating sites. They will assign a classification of Definite TB, Probable TB, Possible TB or non-TB (see table below) to each participant, as soon as possible after the week 8 follow up time point. Participants started on TB treatment at clinics will be followed up for 6 months to evaluate treatment response. During phase 3 of the study, the committee will remain blind to the point of care TransDot test results on the test cohort, until outcome classification is complete.

| Pos = positive; neg = negative; con = contaminated; GR = good response; PR = poor response; NG = none given | | | | | | | | | |
|---|--------------------|----------------------------------|------------|-----------------|----------|-------------------|--------------|------------------------|----------|
| Category | Culture | GeneXpert | AFB smear | CXR | Symptoms | TB Treatment | TB Treatment | Response to antibiotic | Class |
| | | | | | | started by clinic | response | (AB), if prescribed | |
| Α | pos | | | | pos | | | | Definite |
| В | neg or con | pos (no TB in past year) | | | pos | | | | Definite |
| С | neg or con | neg or pos (TB in past year) | pos | pos | pos | yes | GR | | Definite |
| D | neg or con | neg or pos (TB in past year) | pos | neg | pos | yes | GR | | Probable |
| E | neg or con | neg or pos (TB in past year) | neg | pos | pos | yes | GR | | Probable |
| F | neg or con | neg or pos (TB in the past year) | neg | pos | pos | No | | PR | Possible |
| G | neg or con | pos (TB in past year) | neg | neg | pos | yes | GR | | Possible |
| н | neg | neg | neg | pos | pos | no | | GR | No TB |
| I | neg | neg | neg | neg | pos | no | | NG | No TB |
| 1 | Not done or con | Not done | Not done | | | | | | Exclude |
| К | Not done or con | pos (TB in past year) | pos or neg | neg or not done | pos | yes PR | | | Exclude |
| L | Not done or contam | Pos TB in past year | pos or neg | neg or not done | pos | no | NG | PR | Exclude |

The case definitions will be applied as shown in the table below:

Definitions:

TB symptoms or signs: symptoms volunteered or specifically elicited by interviewer and signs objectively observed by examiner that include

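### The three blinding rules for TransDot results are worded differently and all end at outcome classification, so none protects the week 24 treatment-response outcomes

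*Combined protocol and SAP*

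**What the plan says.** Three places state how long TransDot results are withheld in the test set.

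- Section 4, speaking of the outcome classification committee: "who will remain blinded to the TransDot results of the test set, until after completion of all participants' outcome classification".
- Section 4.2, for phase 3: "the committee will remain blind to the point of care TransDot test results on the test cohort, until outcome classification is complete".
- Section 6.1, under the fingerprick test: "Study investigators will be blinded to the TransDot test results until the final outcome classification has been completed for each participant".

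Section 4.2 adds: "The committee will consist of clinician investigators from the participating sites". It has classes assigned "to each participant, as soon as possible after the week 8 follow up time point", and continues: "Participants started on TB treatment at clinics will be followed up for 6 months to evaluate treatment response". Of the week 8 and week 24 TransDot tests, section 6.1 says: "It will be compared to week 8 and 24 treatment outcomes as defined by sputum results, radiology, where applicable and TB symptoms". Section 6.1 also withholds TransDot results from clinic staff and bars their use in clinical decisions.

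**The concern.** A diagnostic accuracy study needs those who form the reference standard to be ignorant of the index test. Here the committee members are also site investigators, so the section 4 and section 6.1 rules apply to the same people. If a site released each result once that participant was classified, members would learn how TransDot tends to behave while still judging other participants' films and responses.

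The treatment-response objective faces a plainer risk. An investigator who already knows a participant's baseline and week 8 TransDot results could later judge the same participant's week 24 film or response. Agreement between TransDot and that outcome could then partly reflect knowledge of the test.

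**Working it through.** **1. The rules side by side**

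| | Section 4 | Section 4.2 | Section 6.1 |
|---|---|---|---|
| Who is covered | Committee | Committee | Study investigators |
| Which results | Test-set TransDot | Test-set point-of-care TransDot only | TransDot, not further specified |
| When blinding ends | All participants classified | Classification complete, unit not stated | Classification complete *for each participant* |
| Week 24 outcomes mentioned | No | No | No |

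The test set also has laboratory TransDot tests on serum, which section 4.2 does not name. Investigators outside the committee are covered only by section 6.1. The CXR pattern is judged by a research clinician (section 4.2 definitions) and X-ray forms are captured by the study clinician (section 7.1). Neither is said to sit on the committee.

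**2. Two readings of section 6.1**

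*For each participant* may mean *for every participant*, which agrees with section 4. It may also mean one participant at a time. Since classification follows each participant's own week 8 visit, a site could adopt the second reading and believe it had complied.

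**3. Route to the primary endpoint**

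Under both readings a participant's own result stays hidden until that participant is classified. What remains is learning from other participants' results. Room for judgement is also limited. Category A rests on culture and symptoms. Category B rests on GeneXpert without TB in the past year, with symptoms. Categories C to I draw on the CXR reading, in most rows together with treatment or antibiotic response. Of these, D and E count as true positives in the primary analysis and F and G are left out of it (section 10.1), so a shift between rows could matter. Nothing in the documents says how often one would occur.

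**4. Route to the week 24 outcome**

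Inputs: classification soon after week 8 (section 4.2); last visit at week 24 for treated participants (section 4); test set of 300 with about one third TB (section 10.2).

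- Interval from earliest classification to last outcome: 24 − 8 = 16 weeks.
- Expected TB cases in the test set: 300 × 1/3 = 100.

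*Per-participant reading.* Up to about 100 treated participants could have their baseline and week 8 results seen about 16 weeks before the week 24 outcome is judged.

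*Section 4 reading.* Count calendar weeks from the last test-set enrolment. The last classification comes at about week 8 + d, where d ≥ 0 is the committee's delay. A treated participant enrolled t weeks before the last one has the week 24 visit at week 24 − t. That visit falls after the last classification if 24 − t > 8 + d, that is, if t < 16 − d. So at most the treated participants enrolled in the final 16 weeks of test-set recruitment are exposed. The documents do not give the length of that recruitment period, so no count follows.

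The outcome at risk is partly judged. The section 4.2 definition of treatment response includes symptom improvement of at least 50% and CXR improvement. Sputum results leave less room, and week 24 films are taken only when indicated (section 6.2).

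**The case against.** A reader might infer that section 6.1 contradicts section 4. The text does not establish that. The two agree if *each* means *every*, and a committee member who follows section 4 satisfies section 6.1 as well. This objection stands: the defect is an ambiguity to be reconciled.

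A reader might also try to size the primary-endpoint bias by moving some share of discordant participants toward TransDot. That calculation assumes the classifier knows that participant's own result, which both readings exclude. Any share chosen would have no basis in the documents. This objection also stands, and no shift in sensitivity or specificity is claimed here.

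On week 24, it is fair to say that section 6.1 is not the root cause, since section 4 stops at classification too. Nor do the documents say who assigns the week 24 outcome: nurses complete the symptom forms (section 6.1) and the study clinician captures X-ray forms (section 7.1). It could also be argued that *final* classification in section 6.1 means a decision after the six-month follow-up, but no section says so, and section 4.2 sets classification soon after week 8. These points narrow the concern without closing it, because no statement keeps anyone blinded until week 24 outcomes are recorded.

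**Conclusion.** The point holds as an ambiguity with a gap behind it. The ambiguity is whether investigators may see results participant by participant. If they may, the reference standard is exposed only indirectly, to an extent the documents do not allow one to estimate. The gap is that blinding ends at classification under every rule, which leaves the judged parts of the week 24 outcome unprotected.

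The reach is up to about 100 treated test-set participants, some 16 weeks early, on the per-participant reading. Under section 4's rule it is limited to those whose week 24 visit follows the last classification. The figure of 100 assumes that one third of 300 have TB and that all of them are treated and followed to week 24. It counts possible exposure, not bias. A reader might infer that all of these outcomes would be unblinded as planned, but that depends on the disputed reading. The direct consequence is for a secondary objective.

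**What to change.** Put one identical rule in sections 4, 4.2 and 6.1: no investigator, CXR reader or committee member sees any test-set TransDot result, fingerprick or serum, from any visit, until all test-set classifications and all week 24 outcomes are locked. State in the same place who assigns the week 24 outcome. Copying section 4's present rule into section 6.1 would remove the ambiguity but leave the week 24 gap.

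The cost is a sentence in three places, matching access limits on the TransDot field in the study database, and a wait of up to about 16 weeks beyond the last classification before investigators see results. Care is unaffected, because section 6.1 already keeps TransDot out of clinical decisions.

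One limit remains. The research nurse runs the fingerprick test, records its result and completes the symptom forms. The rule therefore protects the classification and radiology judgements but does not fully blind the symptom data, and the study report should say so.
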